Proportional Hazards regression (subject to validity of the 'proportional hazards' assumption) and Kaplan-Meier survival plots. If the proportional hazard assumption is not fulfilled a logrank test will be performed.

Which test to be used in the analyses of secondary efficacy variables depends on the type of variable, e.g., logistic regression for binary variables, proportional odds model for an ordinary scaled variable, analysis of variance (ANOVA) or covariance (ANCOVA) for continuous variables as appropriate. If the underlying assumptions are not fulfilled, data transformation or non-parametric test will be performed. For comparison of proportions, Chi square tests, Fisher's exact test, or Mantel-Haenszel procedures, as appropriate, will be considered. For continuous variables, the Wilcoxon rank-sum test or rank ANOVA/ANCOVA will be used. The STATA or SAS statistical software will be used for the analysis.

EO-5D and VFO25 will be evaluated according to their respective user protocols.

Safety

AEs data will be captured and encoded by system organ class (SOC) and lowest level term (Medical Dictionary for Regulatory Activities, current version). A listing of AEs will be created. This listing, at minimum, will contain a description of AEs as to seriousness, severity, onset date and end date, duration, action taken (if any), outcome and likelihood of drug causation ("relation"). A frequency table will be compiled for AEs by treatment group, SOC, and lowest level term. Frequency tables will be compiled showing the number of subjects per treatment group affected by one or more (related) AEs, including percentages, the total number of AEs per treatment group and the average number of AEs per subject exposed to the respective treatment.

Clinical laboratory tests will be presented with summary statistics. In addition, the tests will be analyzed with ANCOVA (baseline value of respective laboratory test will be included in the model). All results will be regarded as descriptive only. The p-values will be used to flag safety and tolerability variables worthy of further attention.

Null hypotheses:

• No difference between test treatment and reference treatment.

QUALITY CONTROL AND QUALITY ASSURANCE

Detailed information is provided in Section 9 of the full protocol.

ETHICAL ASPECTS

Detailed information is provided in Section 10 of the full protocol.

SCHEDULE OF ASSESSMENTS

Visits ¹	Screening			Tre	eatment	Period		Follow-	up Period	Relapse ³	End-of-study 4
Study Procedure Study Day	-2 to 0 ⁵	0	7 ± 2	14 ± 2	21 ± 2	30 ± 3	60 ± 3 and every 30 ± 5 until resolution	after end of	treatment ²		
Screening/Administrative/Baseline											
Informed consent	X										
Parent(s), legal guardian(s), or legally authorized representative (LAR) Informed consent ⁶	X										
Demographics	X										
Review medical history ⁷	X										
Inclusion/exclusion criteria	X										
Clinical suspicion of an Acanthamoeba infection by typical clinical findings	X										
Confirmation of Acanthamoeba infection by confocal microscopy ⁸	Х										
Corneal scraping ⁹	X									x	
Vital signs 10	X										
Study Drug Administration			•	,							
Randomization 11		X									
Dispense study drug ¹²		х				X	X			x	
Study drug administration ¹³		Х	х	х	Х	Х	X			X	
Efficacy Assessments											
Best corrected visual acuity		\mathbf{x}^{11}									X
Slit lamp examination		\mathbf{x}^{11}	х	X	X	X	X	X	X	X	X
Pupil test (swinging light test) 14		\mathbf{x}^{11}	X	X	X	X	X	X	X	X	X

Visits ¹	Screening			Tre	atment	Period	Follow-	up Period	Relapse ³	End-of-study 4	
Study Procedure Study Day	-2 to 0 ⁵	0	7 ± 2	14 ± 2	21 ± 2	30 ± 3	60 ± 3 and every 30 ± 5 until resolution	after end of	treatment ²		
EQ-5D questionnaire 15,16		\mathbf{x}^{11}	X	X	X	X	X	X	X	X	X
Visual functioning questionnaire (VFQ25) 15,17		\mathbf{x}^{11}	X	X	X	X	X	X	X	X	X
Safety Assessments											
Hematology, biochemistry	X										x
Urinalysis (dipstick)	х										х
Urine pregnancy dipstick (women of childbearing potential only	Х					X	Х	х	X	X	х
Use of topical steroids and oral NSAIDs 18	X				Х						
IOP		\mathbf{x}^{11}	Х	х	Х	х	X	X	X	X	х
Ophthalmoscopy 19		\mathbf{x}^{11}									х
Photography of affected cornea		\mathbf{x}^{11}				х			X		х
Ongoing Subject Review											
Concomitant therapy ⁷	x	X	x	X	Х	X	X	x	X	X	х
Adverse events	х	Х	Х	х	X	X	X	х	X	X	х

- 1. During each visit, subjects will enter the clinical research center and will leave after completion of all assessments.
- 2. If subjects are cured 90 days after end-of-treatment visit, the study-end-point is reached and the End-of-Study assessments will be performed.
- 3. If within 90 days after end-of-treatment and within 11 months (Day 335) after randomization the subject relapses, and cultures are negative for *Acanthamoeba*, treatment with the study drug will be re-started according to the treatment schedule, starting with the Day 0 treatment regime. Assessments and visits will also be restarted at Day 0, Day 30 and all consecutive visits of the treatment phase. A detailed treatment plan and follow-up protocol is provided in Section 5.3.
- 4. End-of-study is defined as: (a) the last follow-up visit at 90 days after end of treatment, (b) the day of study drug unmasking in the event of the subject becoming a Treatment failure, (c) if withdrawn from the trial of other reasons, (d) if a subject has been treated for 12 months after randomization (also a Treatment failure).
- 5. Screening and baseline assessments will take place on Day -2 to 0, before randomization and study drug administration.
- 6. For subjects who have not reached the age of majority (i.e. 18 years of age in most jurisdictions), the subject must provide assent (written or verbal) and the parent/guardian/legally authorized representative must provide written informed consent before the subject's participation in the study.
- 7. All medical and medication history related to the current eye infection will be reported. For the remaining medical and medication history, only the last 30 days before signing the ICF will be reported in the case report form (CRF).
- 8. Confocal microscopy is optional if already performed within 7 days prior to study entry as part of standard care providing the images are available to the Investigator to assess.

- 9. All subjects at screening, meeting the inclusion criteria and including those with negative confocal microscopy findings will have corneal scrapes for culture and histology of *Acanthamoeba*, and to perform *Acanthamoeba* deoxyribonucleic acid (DNA) identification by polymerase chain reaction (PCR). Note: this is being done for study quality, for correlation with confocal microscopy findings, and to identify subjects with fungal and viral infections. Because culturing and PCR will take 2 to 8 days, during which time subjects thought clinically to have *Acanthamoeba* keratitis and would be starting treatment before randomization, this assessment is not part of the inclusion criteria. This assessment is optional if already performed within 7 days prior to study entry as part of standard care. Corneal scraping for culture and histology of *Acanthamoeba*, and to perform *Acanthamoeba* DNA identification by PCR will be repeated in case of a relapse within 90 days after end-of-treatment and within 11 months (Day 355) after randomization.
- 10. Blood pressure, pulse rate and body temperature.
- 11. Before first study drug application.
- 12. Study drug will be provided for 30 days at the Day 0 visit. At other dispensing visits, study drug will be provided for 90 days of treatment.
- 13. On Day 0, the first study drug application will be at the clinical research center. Thereafter, study drug will be self-administered at home. When the subject is at the clinical research center for assessments, subjects will apply the study drug themselves at the clinical research center. On Days 0 to 5, subjects will apply study drug every hour daytime only (1 drop of each ophthalmic solution in the affected eye). On Days 6 to 12, (1 week), subjects will apply study drug every 2 hours daytime only. On Days 13 to 19, (1 week), subjects will apply study drug every 3 hours daytime only. On Day 20 until resolution, subjects will apply study drug 4 times a day at daytime only. Subjects will be treated for the maximum of 1 year after randomization.
- 14. The Pupil test (swinging light test), to detect an afferent pupillary defect, is used to detect retinal or optic nerve involvement when the retina cannot be examined.
- 15. If the subject is unable to complete the questionnaires without assistance, the questionnaires may be verbally answered and the subject's responses recorded by site personnel or a chaperone. When multiple assessments are scheduled at the same time, completion of questionnaires by the subject will be done before the clinical examinations.
- 16. Subjects being ≤15 years of age will complete the youth version of this questionnaire.
- 17. Only to be performed by subjects of \geq 18 years.
- 18. The use of topical steroids and oral NSAIDs is complex and described in the Synopsis and Protocol. For subjects not already using topical steroids or NSAIDs on trial entry these may be introduced at day 21 in subjects whose inflammatory signs are not improving. Please see the Synopsis and Protocol for detailed guidelines.
- 19. Ophthalmoscopy will be performed at baseline on all patients and at any time thereafter if the pupil tests or intraocular pressure are abnormal.

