Efficacy evaluations will consist of assessment of best corrected visual acuity (BCVA), pupil test (swinging light test), slit lamp examination, EuroQol five-dimension scale (EQ-5D) questionnaire, and visual functioning questionnaire 25 (VFQ25).

Safety and tolerability evaluations will consist of adverse event (AE) reporting, clinical laboratory (hematology, biochemistry and urinalysis), intraocular pressure (IOP), ophthalmoscopy, and photography of affected cornea.

Detailed information about adverse event reported is provided in Section 0.

See the Schedule of Assessments on page 22, Section 6 and Appendices 1 to 3 in the full protocol, and the Study Operations Manual for details of the evaluations.

SUBJECT COMPLETION/WITHDRAWAL

Detailed information is provided in Section 4.4 of the full protocol

STATISTICAL METHODS

Protocol section 7 STATISTICAL METHODS, page 57

A statistical analysis plan (SAP) with more technical and detailed elaboration of the principal features of the proposed statistical analysis, presentations and the way in which anticipated analysis problems will be handled, will be written before the code is broken. See Section 7 for detailed information.

Sample Size Determination

From the results of the sponsor's observational, case series retrospective study 038/SI, a CRR_12 of 67% for the conventional combination therapy is expected. This figure is in the range of cure rates described in the literature. If the true difference in CRR_12 is 0.20 (Δ) (or more) in favor of PHMB monotherapy (0.08% PHMB), a total sample size of 116 subjects (allowing for 10% loss to follow-up) should give the study at least 80% power to detect superiority, with 2-sided alpha=0.10 (or equivalently 1-sided alpha=0.05).

Assuming a prevalence of late stage diseases in 38% of subjects, the expected CRR_12 in the control group will be reduced from 67% to 63%. To account for the inclusion of this group, the sample size has been adjusted to 130 subjects (allowing for 10% loss to follow-up).

Efficacy

All efficacy evaluations will be based on the Full Analysis Set. Moreover, the primary efficacy variable, CRR_12, will be evaluated also for the Per-Protocol Analysis Set.

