Since it is also possible to test for non-inferiority if the superiority hypothesis is not met, additional conditions are specified (see list below) to meet the strict requirements of a non-inferiority study, making it feasible to test for non-inferiority using the results from the superiority analysis, without a further separate analysis. The 90% confidence interval for the difference between the treatments obtained from the superiority analysis gives the necessary information. Position of the lower end of the confidence interval relative to a pre-defined agreed 0.20 non-inferiority margin (Δ) provides the key information for making decisions (conclusions) about non-inferiority. The additional conditions specified to make testing for non-inferiority feasible are the following:

- Pre-defined non-inferiority margin (Δ=0.20) based on both clinical and statistical considerations, i.e., chosen
 on the basis of external information and not chosen to fit the data.
- Analysis of the Full Analysis Set (FAS) and the Per-Protocol Analysis Set (PPAS), giving similar results with respect to p-values and confidence intervals for the efficacy measure at issue.
- Study design and implementation directed at minimizing deviation from protocol (a particularly important source of bias in non-inferiority studies), e.g., special care to minimize violations of: entry criteria; non-compliance; withdrawals; loss; missing data; etc. This should help ensure the second bullet point.
- Evidence that the standard treatment is showing its usual (expected) level of efficacy.

These specifications are in accord with the recommendations by the Committee for Proprietary Medicinal Products (CPMP) 482/99.

Null hypothesis superiority:

• No difference between test treatment and reference treatment

Non-inferiority clinical studies aim to demonstrate that the test treatment is no worse than the reference by more than a pre-specified small amount.

Null hypothesis non-inferiority:

• Test treatment is inferior to the reference by Δ or more

CRR_12 will be analyzed with a logistic regression model and model-based estimates of the difference between treatments, odds ratio with corresponding confidence intervals and p-values will be provided. Time-to-event (clinical resolution) analysis will also be performed for the comparison of CRR_12s between treatments, including the Cox

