5.1 Sample Size

A total of 130 subjects affected by *Acanthamoeba* keratitis will be assigned to one of the above two treatment groups in a ratio of 1:1.

The protocol states, in section 7.6:

"From the results of the sponsor's observational, case series retrospective study 038/SI, a CRR_12 of 67% for the conventional combination therapy of PHMB 0.02% and propamidine 0.1% is expected. This figure is in the range of cure rates described in the literature. If the true difference in CRR_12 is 0.20 (Δ) (or more) in favour of PHMB monotherapy (0.08% PHMB), a total sample size of 116 subjects (allowing for 10% loss to follow-up) should give the study at least 80% power to detect superiority, with 2-sided alpha=0.10 (or equivalently 1-sided alpha=0.05).

LINK Medical Study ID: PSR012

Assuming a prevalence of late stage disease, and worse outcomes, in 38% of subjects, the expected CRR_12 in the control group will be reduced from 67% to 63%. To account for the inclusion of this group, the sample size has been adjusted to 130 subjects (allowing for 10% loss to follow-up, i.e. 116 evaluable subjects).

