7.9.1 Primary Efficacy Variable

The main endpoint disease resolution 12 months after baseline will be assessed at each visit up to study day 365.

Clinical resolution 12 months after baseline for a patient is defined as:

The percentage of subjects cured 30 days after discontinuing all study therapies, within 12 months of randomization. A clinical resolution classification requires a Yes response to the eCRF variable CRYN question: "Was clinical resolution obtained?" at one of the study visits from day 1 up to study day 365 in combination with a response *No* to the eCRF variable RELAPYN question "Did the subject experience relapse since the last visit?" at the pursuing visits, up to the last recording of this information. There should be no relapses after (the last) clinical resolution classification. Discontinued subjects will be regarded as not cured.

For patients defined as fulfilling disease resolution within 12 months, the date of the visit at which annotated CRYN is first answered with a Yes will be used as the date of resolution. The time-to-cure secondary variable will be the number of days from randomisation to the visit where resolution was recorded.

Since it is also possible to test for non-inferiority if the superiority hypothesis is not met, additional conditions are specified (see list below) to meet the strict requirements of a non-inferiority study, making it feasible to test for non-inferiority using the results from the superiority analysis, without a further separate analysis. The 90% CI for the difference between the treatments obtained from the superiority analysis gives the necessary information. Position of the lower end of the CI relative to a pre-defined agreed 0.20 non-inferiority margin (Δ) provides the key information for making decisions (conclusions) about non-inferiority.

PHMB has received the orphan drug designation. The use of 90% CI for the difference between the two treatments is to provide a 95% lower CI limit for non-inferiority.

The additional conditions specified to make testing for non-inferiority feasible are the following:

- Pre-defined non-inferiority margin (Δ =0.20) based on both clinical and statistical considerations, i.e., chosen on the basis of external information and not chosen to fit the data.
- Analysis of the FAS and the PPAS, giving similar results with respect to p-values and CIs for the
 efficacy measure at issue.

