- Study design and implementation directed at minimizing deviation from protocol (a particularly important source of bias in non-inferiority studies), e.g. special care to minimize violations of: entry criteria; non-compliance; withdrawals; loss; missing data; etc. This should help ensure the second bullet point.
- Evidence that the standard treatment is showing its usual (expected) level of efficacy.

These specifications are in accord with the recommendations by the Committee for Proprietary Medicinal Products, in document *Points to consider on switching between superiority and non-inferiority* (CPMP) 482/99. The recommendation regarding similar results with respect to p-values and CIs is founded on that the FAS "is generally not conservative and its role should be considered very carefully" in non-inferiority trials.

Null hypothesis difference:

No difference between test treatment and reference treatment

Non-inferiority clinical studies aim to demonstrate that the test treatment is no worse than the reference by more than a pre-specified small amount.

Null hypothesis non-inferiority:

• Test treatment is inferior to the reference by Δ or more

CRR_12 will be analysed using a general linear model (GLM) approach with treatment as factor to estimate the difference between success rates for the treatments, and test for difference between treatments. This will be the primary test of efficacy. The new treatment will be declared as non-inferior to the 0.02% PHMB + 0.1% propamidine combination therapy, if the lower limit of the 95% CI satisfies the requirement of a non-inferiority margin of Δ =0.20. The effects of covariate variables on the success rate will also be assessed using the GLM model with treatment, age and sex as explanatory variables. Further explorative analyses will be conducted by adding other, selected variables such as steroid use before treatment start, to the GLM model.

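### Non-inferiority is read from an FAS analysis that scores every discontinued subject as not cured; if that bound alone decides, 10% equal loss lifts the false non-inferiority rate from 4.5% to at most about 7%, and the FAS/PPAS condition is too loose to prevent it.

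*Protocol*

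**What the plan says.** The trial tests superiority first and may fall back on non-inferiority with a margin of 0.20. The protocol (Synopsis, Statistical Methods; section 7.4.1) and SAP 7.9.1 list conditions meant to meet non-inferiority standards, "making it feasible to test for non-inferiority using the results from the superiority analysis, without a further separate analysis". The lower end of the 90% interval from the superiority analysis is compared with the margin. One condition is that FAS and PPAS give similar p-values and intervals. SAP 7.9.1 explains why: in a non-inferiority trial the FAS "is generally not conservative and its role should be considered very carefully".

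On missing outcomes, SAP 7.9.1 says: "Discontinued subjects will be regarded as not cured". Protocol 4.4 counts loss to follow-up among the reasons for discontinuation. SAP 7.2 removes subjects who never reach the day 30 visit from the efficacy sets, and the FAS requires an assessed primary variable. The sample size treats losses differently again, as subjects who cannot be evaluated: "allowing for 10% loss to follow-up, i.e. 116 evaluable subjects" (SAP 5.1).

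SAP 7.9 calls the PPAS analysis supportive. SAP 7.2.2 leaves the choice of excluding deviations to the clean file meeting. The decision sentence in SAP 7.9.1 refers to the lower limit of a 95% interval and names no second analysis set. SAP 7.1.5 points to sensitivity analyses under each variable, but 7.9.1 contains none for losses.

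**The concern.** Scoring a protocol treatment failure as not cured is right. Giving the same score to a subject who moved away puts the same share of artificial failures into both arms and multiplies the true difference by (1 - loss). In a superiority test with equal losses this costs power and does not raise the error rate. In a non-inferiority test it pulls a treatment that is truly 0.20 worse inside the margin. Poor follow-up then makes the fallback claim easier to win. That claim could support first-line use of the monotherapy, so its error rate should not depend on how many subjects are lost.

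**Working it through.** **Inputs.** Control cure 0.63 after the late-stage adjustment, target difference 0.20, two-sided alpha 0.10, power 80%, 10% loss, 130 randomised 1:1, so 65 per arm (Protocol 7.6, SAP 5.1). Margin 0.20 with a 90% interval (Protocol 7.4.1). Assumed here: losses are unrelated to outcome and equal between arms, and the quantity of interest is cure had the subject been followed.

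**The plan's own figure.** n per arm = [p1(1-p1) + p2(1-p2)] × (1.645 + 0.842)² / 0.20².
- 0.67 v 0.87: 0.3342 × 6.18 / 0.04 = 51.7, so 52 per arm and 104 evaluable; 104 / 0.9 gives 116.
- 0.63 v 0.83: 0.3742 × 6.18 / 0.04 = 57.8, so 58 per arm and 116 evaluable; 58 / 0.9 gives 65 per arm, 130 in all.

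Both totals match. They divide by 0.9, so the sizing removes lost subjects and does not score them as failures.

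**False non-inferiority when the FAS bound decides.** Put the truth at the margin: test 0.43, control 0.63. With a share L lost and scored as not cured, the arms become 0.43(1-L) and 0.63(1-L), and the difference is -0.20(1-L). Lower bound = observed difference - t(0.95; 128 df) × residual SD × √(2/65), from the linear model with treatment as factor. The table sums the two binomial distributions over all outcomes whose bound lies above -0.20.

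| Loss in each arm | Expected difference | Linear model | Wald |
|---|---|---|---|
| 0% | -0.20 | 4.5% | 4.5% |
| 5% | -0.19 | 5.8% | 5.8% |
| 10% | -0.18 | 7.2% | 7.2% |
| 15% | -0.17 | 8.9% | 9.0% |
| 20% | -0.16 | 10.9% | 11.1% |

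Hand check at 10%: SE = √[(0.387 × 0.613 + 0.567 × 0.433)/65] = 0.086. The shift is 0.02/0.086 = 0.23 SE, and P(Z > 1.645 - 0.23) = 7.9%, against 5.0% with no loss on the same approximation. The Newcombe interval gives 5.0% rising to 7.8%.

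**Half the losses before day 30.** Then 5% leave the FAS (65 × 0.95 is about 62 per arm) and the difference is -0.20 × 0.90/0.95 = -0.189. The rate is 6.1% with 61 per arm and 6.6% with 62.

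**Two-sided 95% interval.** The rate goes from 2.0% at no loss to 3.5% at 10% loss.

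**If FAS and PPAS both had to exclude -0.20.** With followed subjects standing in for the PPAS, 1,000,000 simulated trials at 10% loss give 7.2% passing in the FAS, of which 3.2 points fail in the followed subjects. The joint rate is about 4.1%. It is also 4.1% at 20% loss. The two lower bounds typically differ by only about 0.03.

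**Unequal losses (Wald).** With 5% lost on test and 15% on control, false non-inferiority is 20.0% and false superiority 17.5%. With the imbalance reversed, they are 1.9% and 0.9%.

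**The case against.** The strongest reply is that the plan anticipates this bias. The sentence about a shared analysis depends on listed conditions. One requires FAS and PPAS to agree, for the very reason that the FAS is not conservative here; another asks for special care over withdrawals, loss and missing data. SAP 7.4 lists missing the two follow-up visits as a major deviation, so the PPAS may come close to a followed-subjects set. An FAS bound inside the margin with a PPAS bound outside it would be hard to call similar. A reader might infer that the plan ignores the problem, or that its error rate simply is 7%. The documents support neither.

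The reply falls short because the condition has no operating rule. Similarity is given no criterion, and bounds about 0.03 apart could pass. The PPAS is only supportive, and its exclusions are still to be settled. Under SAP 7.2.2 a resolution not confirmed at the 30- and 90-day follow-ups counts as not resolved, so the PPAS can carry the same dilution. Read literally, the missed-visits deviation could also remove true failures, who exit the trial and would normally miss those visits.

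Three further limits stand. Losses before day 30 leave the efficacy sets, so 7.2% is a ceiling for 10% equal loss. SAP 7.9.1 presents the 90% interval as giving a 95% lower limit, so a one-sided 95% bound is the likely meaning, but the 95% wording can be read as two-sided. And if being discontinued is itself meant to be an unfavourable outcome, there is no inflation; the plan does not say so, and its sizing treats these subjects as not evaluable.

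**Conclusion.** The point holds in limited form. Followed as written, the plan can claim non-inferiority from an FAS bound that scores non-failure losses as not cured. If that bound decides, the one-sided error is at most about 7% at 10% equal loss, against 4.5% with none: about 6% if half the losses are early, and 3.5% under a two-sided 95% interval. The FAS/PPAS condition would bring it to about 4% only under a joint rule, with a PPAS free of non-failure losses. Neither is specified.

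The figures assume 65 per arm, control cure of 0.63 and losses unrelated to outcome. Using 0.67 for control gives the same 4.5% and 7.2%.

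A reader might also infer that the scoring rule is always safe for superiority. It is safe only when losses are balanced; heavier loss on control raises false superiority as well.

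**What to change.** Before the code is broken, amend SAP 7.9.1, with matching wording in the protocol Synopsis and section 7.4.1:

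1. Keep protocol treatment failures as not cured. For the non-inferiority decision, add an FAS analysis that multiply imputes, within arm, subjects lost or withdrawn for reasons other than failure. State which discontinuation reasons in Protocol 4.4 fall in that group; intolerance and adverse events need an explicit choice because they may be related to treatment.
2. Replace the similarity condition with a rule: the one-sided 95% lower bound must exceed -0.20 in the planned FAS analysis, in the imputed analysis and in the PPAS. Remove the statement that no separate analysis is needed.
3. Report the imputed analysis for superiority too, since unequal losses can bias that test.
4. Reconcile the 90% and 95% intervals in SAP 7.9.1.

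The cost is one extra model run and a protocol wording amendment, which SAP section 2 calls for when principal features change. At equal 63% cure and 10% loss, non-inferiority power is about 73% in the planned FAS and 72% in followed subjects, who stand in for the imputed analysis. Requiring both costs more: in the same simulation 73.3% pass in the FAS and 6.0 points of these fail in followed subjects, leaving 67.3%. The PPAS requirement may lower this further, depending on who is excluded.
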